#### 10.3.2. Safety Analyses

All safety analyses will be performed on the ITT Population.

Endpoint	Statistical Analysis Methods
Primary	
The primary endpoint is incidence and type of AEs/SAEs. This endpoint will be summarized using the following two approaches:
 
 
1. Summary statistics will be provided for the integration of the groups and for each group separately (only FF/UMEC/VI 100/62.5/25 mcg, only FF/UMEC/VI 200/62.5/25 mcg and switching medication from FF/UMEC/VI 100/62.5/25 mcg to FF/UMEC/VI 200/62.5/25 mcg).
 
2. Summary statistics will be provided by the dose received at the time of experiencing the AE. (FF/UMEC/VI 100/62.5/25 mcg and FF/UMEC/VI 200/62.5/25 mcg)
 
 
The number and proportion of subjects experiencing at least one AE will be calculated and presented by system organ class (SOC) and by preferred term (PT). Summary statistics will also be presented for all AEs, treatment-related AEs, SAEs, AEs leading to treatment or study discontinuation, and AESI.

Secondary	
Secondary endpoints will be summarized using the approach described in approach 1 above (i.e., provided for only FF/UMEC/VI 100/62.5/25 mcg, only FF/UMEC/VI 200/62.5/25 mcg and switching medication from FF/UMEC/VI 100/62.5/25 mcg to FF/UMEC/VI 200/62.5/25 mcg).
 
Specific details will be provided in the Reporting and Analysis Plan (RAP).

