
 
• Immediately discontinue study treatment
 
• Report the event to GSK within 24 hours
 
• Complete the liver event CRF and complete an SAE data collection tool if the event also meets the criteria for an SAE
 
• Perform liver event follow up assessments (see Follow Up Assessments )
 
• Monitor the participant until liver chemistries resolve, stabilize, or return to within baseline (see MONITORING below)
 
• Do not restart/rechallenge participant with study treatment unless allowed per protocol and GSK Medical Governance approval is granted
 
• If restart/rechallenge not allowed or not granted, permanently discontinue study treatment and may continue participant in the study for any protocol specified follow up assessments
 
 
MONITORING:
 
For bilirubin or INR criteria:
 
 
• Repeat liver chemistries (include ALT, AST, alkaline phosphatase, bilirubin) and perform liver event follow up assessments within 24 hrs
 
• Monitor participants twice weekly until liver chemistries resolve, stabilize or return to within baseline
 
• A specialist or hepatology consultation is recommended
 
 
For All other criteria:
	
 
• Viral hepatitis serology
 
• Obtain INR and recheck with each liver chemistry assessment until the transaminases values show downward trend
 
• Only in those with underlying chronic hepatitis B at study entry (identified by positive hepatitis B surface antigen) and quantitative hepatitis B DNA
 
• Blood sample for pharmacokinetic (PK) analysis, obtained within 72 hours after last dose
 
• Serum creatine phosphokinase (CPK) and lactate dehydrogenase (LDH).
 
• Fractionate bilirubin, if total bilirubin <math>\geq</math> 2xULN
 
• Obtain complete blood count with differential count of leukocytes to assess eosinophilia
 
• Record the appearance or worsening of clinical symptoms of liver injury, or hypersensitivity, on the AE report form
 
• Record use of concomitant medications on the concomitant medications report form including acetaminophen, herbal remedies, other over the counter medications.
 
• Record alcohol use on the liver event alcohol intake case report form
 
 
For bilirubin or INR criteria:
 
 
• Anti-nuclear antibody, anti-smooth muscle antibody, Type 1 anti-liver kidney microsomal antibodies, and quantitative total immunoglobulin G (IgG or gamma globulins).
 

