2. SUMMARY OF KEY PROTOCOL INFORMATION

2.1. Changes to the Protocol Defined Statistical Analysis Plan

There were no changes or deviations to the originally planned statistical analysis specified in the protocol (Dated: 13/MAR/2017), amendment 1 (Dated:24/MAY/2017) or amendment 2 (Dated: 25/OCT/2017).

In order to comply with regulatory guidance where the protocol referred to “Subjects” the analysis plan refers to “Participants”, with the exception of displays and study populations.

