8.2. Adverse Events Analyses

Adverse events analyses including the analysis of adverse events (AEs), Serious (SAEs) and other significant AEs will be based on GSK Core Data Standards. The details of the planned displays are provided in [Appendix 11: List of Data Displays](#).

All AEs will be classified using the standard GSK Medical Dictionary for Regulatory Activities (MedDRA) dictionary, and grouped by SOC and PT, unless otherwise stated. The investigator will evaluate all AEs with respect to seriousness, severity, and causality.

The tabular summary for each type of AE listed below will include the number of participants who reported at least one event, and percentage of participants who reported at least one AE (incidence) for each SOC (where applicable), each PT, and overall. By default, adverse events will be sorted by MedDRA SOCs, in descending order from the SOC with the highest total incidence (i.e., summed across all dose groups) for any adverse event within the class, to the SOC with the lowest total incidence. If the total incidence for any two or more adverse events is equal, the events will be presented in alphabetical order. Only SOCs with observed AE PTs will be presented. Repeat sort order for MedDRA PTs within each SOC.

In principle, all safety analyses will be provided by dose group and total. However, due to Japan regulatory authority requirement, AE analyses by dose at the time of onset of the AE will be prepared in final analyses of this study. Note that dose at the time of onset of the AE will be decided by allocated dose even if a given subject has incorrect study treatment in certain period (but not during all period). If a given subject has incorrect study treatment during all period, then this subject will be analysed according to the treatment which he/she received. In interim analyses, selected tables will be provided. Please refer to Section [11.11.5](#).

Each type of the following will be summarized for both approaches (i.e., by dose group and total, by dose at the time of onset of the AE)

- AE overview during treatment period
- All AEs during treatment period (by SOC and PT; by SOC and PT and maximum severity)
- Drug related AEs during treatment period (by SOC and PT; by SOC and PT and maximum severity)
- Serious AEs during treatment period (by SOC and PT)
- AEs resulting in withdrawal from study (by SOC and PT)

- AEs of Special Interest during treatment period (by SOC and PT)

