11.11.5. Safety Tables (interim)

Safety: Tables					
No.	Population	IDSL / Example Shell	Title	Programming Notes	Deliverable [Priority]
Treatment Exposure					
2.1.	ITT	EX1	Summary of Exposure to Study Treatment (Interim)	ICH E3	IA [1]
Adverse Events (AEs)					
2.2.	ITT	AE13	Summary of All Adverse Events Overview During Treatment Period (Interim)	ICH E3	IA [1]
2.3.	ITT	AE1	Summary of All Adverse Events During Treatment Period (Interim)	ICH E3	IA [1]
2.4.	ITT	Study Specific	Summary of All Adverse Events During Treatment Period per Thousand Person-Year (Interim)		
2.5.	ITT	AE5A	Summary of All Adverse Events During Treatment Period by maximum severity (Interim)	ICH E3	IA [1]
2.6.	ITT	AE1	Summary of All Drug-Related Adverse Events During Treatment Period (Interim)	ICH E3	IA [1]
2.7.	ITT	Study Specific	Summary of All Drug-Related Adverse Events During Treatment Period per Thousand Person-Year (Interim)		IA [1]
2.8.	ITT	AE3	Summary of Most Common Adverse Events (3% or more of Subjects in Any Treatment Group) During Treatment Period by dose group (interim)	ICH E3 3% or more of Subjects in Any Treatment Group	IA [1]
2.9.	ITT	Study Specific	Summary of Adverse Events for week 0-12 and week 13-24 During Treatment Period (interim)		IA [1]

CONFIDENTIAL

207236

Safety: Tables					
No.	Population	IDSL / Example Shell	Title	Programming Notes	Deliverable [Priority]
2.10.	ITT	AE15	Summary of Common (>=5%) Non-serious Adverse Events by System Organ Class and Preferred Term During Treatment Period (Number of Participant and Occurrences) (Interim)	FDAAA, EudraCT 'Common' to be defined by study/project team. For studies with very few events/participants, listing is sufficient: discuss this option with your disclosure representative.	IA [1]
Serious and Other Significant Adverse Events					
2.11.	ITT	AE1	Summary of Serious Adverse Events During Treatment Period (Interim)		IA [1]
2.12.	ITT	Study Specific	Summary of Serious Adverse Events During Treatment Period per Thousand Person-Year (Interim)		IA [1]
2.13.	ITT	AE1	Summary of Adverse Events Leading to Withdrawal from Study During Treatment Period (Interim)		IA [1]
2.14.	ITT	AE1	Summary of Adverse Events of Special Interest During Treatment Period (Interim)		IA [1]
2.15.	ITT	Study Specific	Summary of Adverse Events of Special Interest During Treatment Period per Thousand Person-Year (Interim)		IA [1]

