12.17.	ITT	AE3	Summary of Most Common Adverse Events (3% or more of Subjects in Any Treatment Group) During Treatment Period by dose at AE (dose: FF/UMEC/VI 200/62.5/25)	ICH E3	SAC [1]
12.18.	ITT	Study Specific	Summary of Adverse Events for week 0-12, week 13-24, week 25-36 and week 37-52 During Treatment Period by dose group		SAC [1]
12.19.	ITT	Study Specific	Summary of Adverse Events for week 0-24, week 25-52 During Treatment Period by dose group		SAC [1]
12.20.	ITT	AE15	Summary of Common (>=5%) Non-serious Adverse Events by System Organ Class and Preferred Term During Treatment Period (Number of Participant and Occurrences)	FDAAA, EudraCT 'Common' to be defined by study/project team. For studies with very few events/participants, listing is sufficient: discuss this option with your disclosure representative.	SAC [1]
12.21.	ITT	AE3	Summary of Non-Serious Drug-Related Adverse Events During Treatment Period by dose group	PLS	SAC [1]
12.22.	ITT	AE1	Summary of All Drug-Related Adverse Events During Treatment Period and Follow-Up Period by dose group		SAC [1]

CONFIDENTIAL

207236

Safety: Tables					
No.	Population	IDSL / Example Shell	Title	Programming Notes	Deliverable [Priority]
Serious and Other Significant Adverse Events					
12.23.	ITT	AE1	Summary of Serious Adverse Events During Treatment Period by dose group		SAC [1]
12.24.	ITT	AE1	Summary of Serious Adverse Events During Treatment Period by dose at AE (dose: FF/UMEC/VI 100/62.5/25)		SAC [1]
12.25.	ITT	AE1	Summary of Serious Adverse Events During Treatment Period by dose at AE (dose: FF/UMEC/VI 200/62.5/25)		SAC [1]
12.26.	ITT	Study Specific	Summary of Serious Adverse Events During Treatment Period per Thousand Person-Year by dose group		IA [1]
12.27.	ITT	AE1	Summary of Adverse Events Leading to Withdrawal from Study During Treatment Period by dose group		SAC [1]
12.28.	ITT	AE1	Summary of Adverse Events Leading to Withdrawal from Study During Treatment Period by dose at AE (dose: FF/UMEC/VI 100/62.5/25)		SAC [1]
12.29.	ITT	AE1	Summary of Adverse Events Leading to Withdrawal from Study During Treatment Period by dose at AE (dose: FF/UMEC/VI 200/62.5/25)		SAC [1]
12.30.	ITT	AE1	Summary of Adverse Events of Special Interest During Treatment Period by dose group		SAC [1]
12.31.	ITT	AE1	Summary of Adverse Events of Special Interest During Treatment Period by dose at AE (dose: FF/UMEC/VI 100/62.5/25)		SAC [1]

CONFIDENTIAL

207236

Safety: Tables					

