No.	Population	IDS / Example Shell	Title	Programming Notes	Deliverable [Priority]
62.	ITT	AE8	Listing of Non-Fatal Serious Adverse Events	ICH E3 Fatal and Non-Fatal SAEs are combined into a single listing for ClinPharm studies (i.e., "Listing of Serious Adverse Events").	SAC [1]
63.	ITT	AE14	Listing of Reasons for Considering as a Serious Adverse Event	ICH E3	SAC [1]
64.	ITT	AE8	Listing of Adverse Events Leading to Withdrawal from Study / Permanent Discontinuation of Study Treatment	ICH E3	SAC [1]
65.	ITT	AE8	Listing of Adverse Events of Special Interest	ICH E3 Required for studies where interventions other than withdrawal from treatment or study are possible.	SAC [1]
Hepatobiliary (Liver)					
66.	ITT	MH2	Listing of Medical Conditions for Participants with Liver Stopping Events	IDS	SAC [1]
67.	ITT	SU2	Listing of Substance Use for Participants with Liver Stopping Events	IDS	SAC [1]
68.	ITT	LIVER5	Listing of Liver Monitoring/Stopping Event Reporting	IDS	SAC [1]

CONFIDENTIAL

207236

ICH: Listings					
No.	Population	IDSL / Example Shell	Title	Programming Notes	Deliverable [Priority]
All Laboratory					
69.	ITT	LB5	Listing of Chemistry Values for Subjects with Any Value Outside Normal Range	ICH E3 May be split into separate listings by chemistry, hematology, etc. Display ALL labs for a subject who experienced a value of potential clinical importance.	SAC [1]
70.	ITT	LB5	Listing of Haematology Values for Subjects with Any Value Outside Normal Range	ICH E3 May be split into separate listings by chemistry, hematology, etc. Display ALL labs for a subject who experienced a value of potential clinical importance.	SAC [1]
71.	ITT	UR2A	Listing of Urinalysis Data (Protein and Occult Blood)	Protein and occult blood only. All subjects data need to be displayed.	SAC [1]
ECG					
72.	ITT	EG3 (modified)	Listing of ECG Values for Subjects with any Abnormal ECG Finding	IDSL Required for ClinPharm studies only.	SAC [1]
73.	ITT	EG5	Listing of Abnormal ECG Findings	IDSL Required for ClinPharm studies only.	SAC [1]

CONFIDENTIAL

207236

ICH: Listings					
No.	Population	IDSL / Example Shell	Title	Programming Notes	Deliverable [Priority]
Vital Signs					
74.	ITT	VS4	Listing of Vital Signs	IDSL Required for ClinPharm studies only.	SAC [1]

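### The SAP's discontinuation AE tables select on study withdrawal alone, where the protocol asks for treatment or study discontinuation: a minor, undeclared narrowing

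*SAP*

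**What the plan says.** The statistical methods for the primary endpoint in protocol 10.3.2 state: "Summary statistics will also be presented for all AEs, treatment-related AEs, SAEs, AEs leading to treatment or study discontinuation, and AESI". The category has two limbs, stopping treatment and leaving the study.

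SAP 8.2 lists the AE types to be summarised by dose group and by dose at onset. The matching entry is "AEs resulting in withdrawal from study (by SOC and PT"), which has only the second limb. The display list follows it:

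- Interim Table 2.13 is "Summary of Adverse Events Leading to Withdrawal from Study During Treatment Period (Interim").
- Final Table 12.27 is "Summary of Adverse Events Leading to Withdrawal from Study During Treatment Period by dose group".
- Final Tables 12.28 and 12.29 repeat this for each strength, by dose at AE.

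The wider category does appear in the SAP, but as a listing. Final Listing 64 is "Listing of Adverse Events Leading to Withdrawal from Study / Permanent Discontinuation of Study Treatment", and interim Listing 21 has the same title.

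SAP 2.1 says: "There were no changes or deviations to the originally planned statistical analysis specified in the protocol".

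**The concern.** AE incidence is the primary endpoint of an uncontrolled, open-label safety study with no hypothesis tests, so the descriptive AE tables are the result. AEs that end treatment are one of the categories the protocol names for that endpoint. The SAP drops one limb of the definition without saying so, and Table 2.13 belongs to the Week-24 summary intended for the JNDA.

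The narrower set lies inside the protocol's set. Any difference therefore runs one way: the tables could undercount AE-related discontinuations but could not overcount them. The clearest candidates are liver stops, which protocol 8.1 lists among the mandatory reasons for ending treatment.

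**Working it through.** The plan states no figure that depends on this point. The check compares texts and ends with one line of arithmetic.

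**1. Do the tables have one condition or two?** The SAP display list has four SOC/PT discontinuation tables (2.13, 12.27, 12.28, 12.29), all titled for study withdrawal. None is titled for treatment discontinuation. Two listings (21 and 64) cover both. The SAP thus uses two conditions in its listings and one in its tables.

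**2. Do the two conditions select the same participants?**

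- Protocol 8.1.3 makes study withdrawal mandatory once study treatment is stopped, without qualification. Under that rule every AE that ends treatment also ends participation, and the SAP tables capture the protocol's set.
- Protocol Appendix 6 covers a liver stopping event where restart is not allowed or not granted, and says to "permanently discontinue study treatment and may continue participant in the study for any protocol specified follow up assessments". Protocol 8.1.4.1 rules out restart after any liver stop in this study, so this branch applies to every such case. It allows treatment to end without study withdrawal.
- Protocol Appendix 4 presents stopping treatment and leaving the study as alternatives for a participant who becomes pregnant. It also says that pregnancy itself is not an AE, so only a complication or a termination could reach an AE table. This example is weak.
- The CRF is not in the documents. If it records the action taken with treatment and the withdrawal from the study separately, the two flags could disagree.

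**3. Where would a divergent case still be seen?** Take an AE recorded at a liver stop in a participant who is kept in the study.

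- It is absent from Tables 2.13 and 12.27 to 12.29.
- It is present in Listings 21 and 64. With onset in the treatment period, it is also in the all-AE tables.
- The participant counts in the treatment-status tables (1.2 and 11.2), which give reasons for stopping but no SOC or PT.
- The AE overview (Tables 2.2 and 12.2, shell AE13) is unknown, because the shell's rows are not shown.

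The listings do not replace the tables. The protocol asks for summary statistics, and SAP 8.2 says the AE listings carry dose group and not dose at AE. A participant who switched strength at Week 24 would therefore not be assigned to a dose at onset there.

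**4. Size.** Assume all 110 planned participants take at least one dose.

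- Effect of one omitted case on the overall incidence: 1/110 = 0.0091, or 0.9 percentage points.
- Under 8.1.3 applied strictly: 0 cases, 0 points.
- Expected drop-outs for any reason at the protocol's rate of about 10%: 110 × 0.10 = 11. The documents do not say how many would be AE-related.
- By strength the denominators are smaller, so one case weighs more. SAP 2.3 sets no target allocation ratio, so that effect cannot be fixed in advance.

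**The case against.** The strongest reply is protocol 8.1.3. It is unqualified, and under it the two categories are the same set. The Appendix 6 sentence is permissive and sits in text that reads as generic, with references to placebo and to studies of hepatic impairment. The schedule of activities has no separate off-treatment visit track beyond the Early Withdrawal visit and the safety contact, and attending those is compatible with having been withdrawn. Little would be hidden in any case: liver stops also have their own listings (23 to 25, 66 to 68 and 89 to 92), and about 11 drop-outs can be checked one by one.

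Most of this stands. It limits the gap to liver stops under one reading of Appendix 6 and to inconsistent CRF coding. It does not remove the mismatch with protocol 10.3.2, nor does it make a listing a summary by dose at AE.

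Three stronger readings are tempting, and the documents do not support them:

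- A reader might infer that such an AE is reported in no discontinuation table at all. That cannot be shown without the AE13 shell.
- A reader might infer that a participant who stops shortly before Visit 7 and then attends it would be counted as a study completer. Protocol 8.1.3 requires that participant to be withdrawn, so the case presupposes a protocol departure.
- A reader might take the separate definitions of treatment and study completion in protocol 5.3, and the SAP's separate disposition tables, as proof that the sets diverge. The converse case, in which treatment is completed but the follow-up contact is missed, is enough to explain them.

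**Conclusion.** The mismatch is real: the SAP narrows a protocol-specified summary of the primary endpoint and declares no change. Its practical effect is small and may be nil, because protocol 8.1.3 normally makes the two sets equal. A live gap needs a liver stop after which the participant is kept in the study, or CRF fields that record the two actions differently. It also needs the event to be recorded as an AE. Each such case would lower the tabulated overall incidence by 0.9 percentage points, assuming 110 treated participants.

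A reader might infer a sizeable relative understatement of AE discontinuations. The documents give neither the number of AE-related stops nor the number likely to be missed, so no relative figure can be supported.

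Severity is minor. The change is still worth making: it cannot alter the tables if the sets coincide, and it prevents an undercount if they do not.

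**What to change.** Define and title the SAP 8.2 bullet and Tables 2.13 and 12.27 to 12.29 by both conditions, permanent stopping of study treatment or study withdrawal, as protocol 10.3.2 requires and as Listings 21 and 64 already do. Separate rows for the two components are optional; the protocol does not ask for them. State whether the AE overview (Tables 2.2 and 12.2) uses the same definition. If the sponsor prefers the narrower tables, SAP 2.1 should declare the change and give the reason.

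Protocol 8.1.3 and Appendices 4 and 6 also contradict one another on whether stopping treatment entails leaving the study, and must be reconciled. Which rule should apply is for the sponsor to settle. The table definition above works under either.

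The cost is one reworded bullet, four titles and one selection condition applied in four tables. No new data should be needed, because the existing listings already require both conditions. The protocol reconciliation is a separate wording clarification.
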